management procedures to handle both suicidal crises, as well as reports of homicidal ideation and risk of child abuse. We will use established protocols from our prior studies conducted with men who have sex with men (MSM) and with individuals at high risk for suicide to guide research staff in responding to crisis or harm situations, including attempting to contact the participant to assess risk level and provide appropriate follow-up (e.g., crisis hotline, safety check, suicide hotline). Staff will be required to contact our full-time clinical counselor ([name]) or clinician ([name]) to manage situations of higher risk. Risk of coercion. Using online recruitment methods where the intervention is not pitched by a recruiter minimizes the risk of potential coercion. Instead, EASM will be able to choose and click on the recruitment advertisement and decide if they wish to learn more or not. Similarly, staff will be trained to discuss all elements of the consent process with potential participants. Consent documents will fully explain the study procedures, potential risks, and potential benefits. Participants will also be reminded that the study participation is voluntary and that refusing to participate in the study or withdrawing from the study is an option at any time. Informed consent documents will be available in English and have grade 5 reading level. Adequacy of Protection against Risks a. Recruitment and Informed Consent We will recruit subjects through the placement of banner advertisements on Facebook and other social media outlets. For those who click on the ad, they will be taken to a page describing the nature of the study: if they then click on interested in participating they will be asked to complete an interest form which will be used by study staff to schedule an in-person visit. During the in-person visit, eligible participants will be given a written informed consent document. We will employ several strategies to offset risks of loss of confidentiality related to participating in our trial. First, we will petition a Certificate of Confidentiality from the Department of Health and Human Services (an explanation will follow indicating that in studies thus covered the researchers have not been forced to release any research data from participants, even under a court order or subpoena). Participants who experience distress during the survey can access our list of community referrals, which can be viewed on our study's application, or contact the research team directly (toll-free number is embedded into the About Us section of the application). Participants can contact study staff to get referrals to local services, and should participants report or display signs of distress during the teleconference interactions they will be asked to speak with a clinician who is a member of the research team. Any unexpected adverse events will be immediately reported to the IRB, and all study activities will halt pending IRB review and recommendations. It will be made clear to all participants in the consent forms that participation in the pilot RCT will not affect their access to any services in their community. The consent document will make it clear that participants can attend any services in their local area and that they do not have to participate in the trial to access services, nor do they have to reveal their participation in the trial to anyone at these agencies. Participants who chose not to participate in the trial will still be able to access the list of local LGBT resources. Participants addresses and any other identifying information will be kept in a separate, password-protected file to avoid risk of identification. All stored data will be kept in a locked room at the University of Pennsylvania. Electronic data will be maintained in a secure server. Access to the data will be located in a folder with restrictions (i.e., may be accessed only by study team members). Access to data will be on a role-based standard; only those study staff that require access to identifying data to complete their study-related roles will be allowed access, as described above. All study staff will be trained in security and confidentiality procedures, and will sign a confidentiality agreement before receiving access to any participant data. We will also develop procedures to minimize indirect disclosure that a participant is enrolled in a study focused on EASMs suicide vulnerability. For each mode of re-contact information,

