
we will ask specifically whether anyone else potentially has access to that mode of communication, and if it is acceptable to leave a non-specific message about participation in a health study. The contact information and permissions will be updated quarterly. No study-related messages will ever mention the nature of the research study. Additionally, all scripts for email, text message, and telephone contact with participants will be reviewed and approved by the University of Pennsylvania IRB before being used for contact with participants. Participants confidentiality will be breached only to protect the safety and welfare of research participants and only in accordance with state and federal law. The exceptions to confidentiality include if the participant reports imminent suicide risk, homicidality, or the physical or sexual abuse of a child. If necessary, authorities will be notified. Although study assessments will not ask about these issues, in the unlikely event that a participant self-discloses this information to study staff, during virtual tele-conference sessions, or through open fields (e.g., additional comments) in the surveys, we will activate our Adverse Events Reporting protocol (see below). These exceptions to breaking confidentiality the case where a participant reveals child abuse, imminent suicide risk, or homicidality will be explained in detail to participants and prior to completing the consent process.

b. Protections against Risk

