
accessible only by study staff. The contact information (name, email address and phone number) in the database will be destroyed at the end of the study, and will never be associated with the study data collected. We will use Norton Clean-Sweep software to delete the database file from the secure server and the back-up file(s) from the separate hard drive.

2. Benefits:

Participants will be asked about sensitive information, yet adequate protections for internet data collection are in place for this study. EASM in the intervention condition may benefit by receiving life skills and suicide prevention content and having a peer trained in MI discussing these topics with them, with the potential to reflect on changing behaviors or taking steps to reduce risk for suicide. Furthermore, participation in the proposed study could potentially benefit participants in a few important ways. First, it is possible that the screening, baseline, and follow-up assessments may be beneficial to all participants by asking them to review their risk behaviors and consider strategies to reduce suicide risk. Therefore, these assessments may actually serve as a very minimal intervention (as could any study assessing risky behaviors). Indeed, young MSM in our prior investigations have commented that they have found the questions to be helpful. Second, participants will have access to the test locator if they desire to reach community organizations providing LGBT-welcoming services in their area. In sum, potential benefits for the research far outweigh the risks for the participants. Others will benefit because the study will result in increased knowledge about suicide prevention interventions to serve those at highest risk for suicidality.

3. Subject Privacy:

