In accordance with the National Institutes of Health (NIH) requirements, we will adopt a Data and Safety Monitoring Plan. We will use the centralized Data Safety Monitoring Board (DSMB) that was developed for the Center. The DSMB will meet regularly to review the study progress, review modifications, and monitor compliance with IRB rules, human subjects procedures and OHRP regulations. The Principal Investigators will provide oversight of all study procedures and quality assurance checks. The data safety and monitoring plan includes the following protocols: All printed records pertaining to the study containing collected data will be securely stored by the Principal Investigators in a locked metal file cabinet housed in the Department of Psychiatry. Electronic files and records will be stored in a firewalled, encrypted server at the University of Pennsylvania; only research staff will have access to this directory. To ensure participants safety as well as the data's validity and integrity, only staff with extensive experience with SGM youth and suicide prevention will be hired. All staff will have signed a confidentiality agreement. We have several mechanisms to ensure the security and integrity of the data. The intervention content, questionnaires, and personal information will be secured with role-based security that will provide different types of users with different access privileges. Further, we will have separate modules as well as separate web-sites (questionnaire and intervention program) to collect personal identifying information, questionnaire data, and to run the actual program. At a high level, the three user types and the associated privileges are: a. Participants will be the actual study participants and, once consented, they will be able to go through the assessments and intervention screens. b. Research Project staff will view/access personal data related to individuals. They will also be able to send e-mails, process subject incentive fees, and email/call participants to remind them of follow-up assessments. c. Research Investigators will be the master users with access to all modules and will be required to use a valid user ID and password to log into/access the system. Penn research staff will be able to maintain users (view/add/modify users), and generate export files for analysis. We will use a unique registration ID for participants and have the rest of their details maintained securely outside of the computer database. Code numbers and contact information will be accessible only to the Research Investigators and Research Project staff. All data will be secured during transmission by using a 256-Bit SSL encryption or higher. The SSL certificate will be from VeriSign or other certificate providers of repute. Critical data fields will be encrypted and stored in the database. The database server itself will be located within the security of the University of Pennsylvania's secure and dedicated firewalls. Mandated breach of confidentiality will occur in the event that a participant is a danger to him or herself or to others or is in danger from others. We will report this in accordance with rules for mandatory reporting. There is a statement in the consent form and assent form notifying participants of this possibility. All study personnel will have either completed the Human Subject Training established by the CITI program. In addition, in compliance with the NIH policy, graduate students and staff will participate in at least 8 hours of mandatory case study and discussions regarding scientific integrity and human subjects. Any additional personnel who may join

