
the project will complete this training before they handle any subject data. Further, issues regarding confidentiality will be reinforced prior to each intervention and data collection with project personnel. Reporting Adverse Events Additionally, all staff will be trained on recognition and documentation of any unusual events or circumstances that occur during data collection. Staff will be trained to report any adverse events that concern them immediately to the Principal Investigators and the University of Pennsylvania IRB. If an adverse event appears to be research-related, it will be reported to the OHRP and the funding institution project officer, along with summaries of discussions concerning the event. The funding institution project officer will be informed of any IRB action taken concerning any adverse event. The Principal Investigators and Project Director will monitor staff closely. Staff deficient in any aspect of performance will be re-trained, closely monitored for proficiency, and if not adhering to established protocols and procedures, will be terminated. No names or other identifying information appear on data documents or in data files as the re-contact information will be stored separately. Only designated staff will have access to the data. The Principal Investigators and Co-Investigators will be responsible for dissemination of study findings through presentations and publications. The Principal Investigators will also be solely responsible for handling any requests from other investigators to examine the data collected during this study.

8. Investigator's Risk/Benefit Assessment:

No more than minimal risk: The risks to research participants enumerated above are reasonable in relation to the anticipated increase in knowledge about suicidal ideation and behaviors among sexual minorities. Our study is expected to result in benefit to society since it will provide a basis of knowledge on which barriers participants face when trying to access services to help them lower their suicide risks. Thus, the unlikely risks entailed by participation in this study are offset by its potential benefits.

INFORMED CONSENT:

1. Consent Process:

Overview

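### The protocol promises action on risk disclosed in open survey fields, but describes no step that brings the text to a staff member's attention

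*Combined protocol and SAP*

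**What the plan says.** The commitment is in RISK/BENEFIT ASSESSMENT, 1. Risks, under a. Recruitment and Informed Consent. Confidentiality may be breached for imminent suicide risk, homicidality, or physical or sexual abuse of a child. If a participant discloses any of these to staff, in a virtual session, or "through open fields (e.g., additional comments) in the surveys, we will activate our Adverse Events Reporting protocol (see below". The same paragraph calls this unlikely and says that the exceptions will be explained before consent is completed.

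The protocol it points to is in 7. Data and Safety Monitoring, under Reporting Adverse Events. There, "all staff will be trained on recognition and documentation of any unusual events or circumstances that occur during data collection", and "Staff will be trained to report any adverse events that concern them immediately to the Principal Investigators and the University of Pennsylvania IRB". That section also says that "Mandated breach of confidentiality will occur in the event that a participant is a danger to him or herself or to others".

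The clinical response is in 1. Risks. On crisis procedures it says "We will use established protocols from our prior studies" to guide staff, "including attempting to contact the participant to assess risk level and provide appropriate follow-up". Staff must contact the counselor or clinician for higher risk. Participants may name up to three emergency contacts, and they receive the Lifeline and study clinician numbers at consent.

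Follow-up surveys are online and self-completed at 2, 4 and 6 months (METHODS, 4. Administration of Surveys and 7. Subject Follow-up). Open fields do exist: the Adoption form (METHODS, 1. Measures) has three open-ended items at each follow-up.

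**The concern.** Every response step starts when a staff member becomes aware of the risk. For a phone call or a peer mentor session that is automatic, because someone is on the line. For text typed into a survey at home, someone has to open the record and read it, and the plan does not say who does so, when, or on what prompt.

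Everyone enrolled reported suicidal ideation in the month before entry. They are told at consent that disclosing imminent risk leads to action. A participant who writes such a disclosure may reasonably believe that it has been seen, and so may not call. If the text waits in a data file, the contact and clinician steps cannot begin.

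**Working it through.** The plan states no figure for this step, so the check has two parts: a search for any mechanism that gets the text read, and the size of the reading task.

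**Candidate mechanisms, and what starts each one**

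- Adverse event reporting (7. Data and Safety Monitoring): reporting is immediate, but it runs from awareness. Recognition during data collection can fairly be taken to include surveys. Free text is not mentioned, and no reading time is set.
- Crisis contact and clinician escalation (1. Risks): starts once risk is known or distress is apparent in a study contact.
- Timed survey actions (METHODS, 4 and 7): the 36-hour reminder, and the hand-over to staff 24 hours after the third notification, apply to surveys that are not completed.
- Dashboard prompts (METHODS, 7): triggered by missed activities.
- Survey flags (1. Risks, b. Protections against Risk; 4. Subject Confidentiality): directed at fraudulent cases.
- Data handling (METHODS, 5. Data Management): download, accumulation and export to an analysis file, with no review of content.
- Support for distress during a survey (1. Risks): the participant must act. The referral list and toll-free number sit in the application. STUDY PROCEDURES, 1. Detailed Description gives the webapp to the experimental arm, so control-arm access to them is unclear.

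None of these brings a submitted comment to a reader.

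**Are staff present?** METHODS, 4 and 7 describe remote completion. STUDY PROCEDURES, 1 says in person, and RESOURCES NECESSARY FOR HUMAN RESEARCH PROTECTION describes completion in the offices, which may mean baseline. Even on site, no one is assigned to read the text.

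**Scheduled interviews.** C-SSRS phone interviews are set for months 2, 4 and 6. Their order relative to the survey is not stated. If the interview comes after the survey, it may detect the risk soon. If it comes first or is missed, the next one is 4 - 2 = 2 or 6 - 4 = 2 months later, and none is scheduled after the 6-month survey. This is a conditional bound, not an estimate of delay.

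**Reading load.** Inputs: 64 participants; three follow-ups; 9-month accrual (CHARACTERISTICS OF THE STUDY POPULATION, 1); 80% retention target. METHODS, 4 ties that target to the first follow-up and METHODS, 7 states it generally; applying it at every wave is an assumption.

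- Total: 64 x 3 = 192 at full completion; 192 x 0.8 = 154 at 80%.
- Window: first 2-month survey at month 2, last 6-month survey at month 9 + 6 = 15, so 13 months. 192/13 = 14.8 and 154/13 = 11.8 a month.
- Peak, months 6 to 11, when all three waves overlap: 64/9 = 7.1 a month; 7.1 x 3 = 21.3, and 21.3 x 0.8 = 17.1.
- If baseline also has open fields: 64 x 4 = 256 at full completion, and the monthly figures above would rise.

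**The case against.** The strongest reply is that what is shown is an unwritten step, not an absent one. Crisis response follows prior-study protocols that are not reproduced, and who opens survey records is often set in an operating procedure. That stands. If a review step exists there, citing it settles the detection part of the point.

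Second, the commitment and the adverse event section, read together, do cover survey text and require immediate reporting. That also stands, from the moment the text is seen. What remains is the time from submission to reading.

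Third, free text is a secondary channel. The C-SSRS interview is the main one, every participant completes a clinician-led safety plan before randomization, and staff have Mental Health First Aid training and weekly supervision. These lower the likely harm, but none gets a comment read.

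A reader might go further in three ways that the documents do not support. One is that there is no crisis response: escalation, emergency contacts and mandated breach are all described. Another is that staff could not trace a comment to a person, because contact details "will be destroyed at the end of the study, and will never be associated with the study data collected". That sentence concerns confidentiality and end-of-study destruction. The plan permits breach to protect participants, and "Code numbers and contact information will be accessible only to the Research Investigators and Research Project staff", so staff hold what they need. The third is that disclosures will wait two months: that needs the interview to precede the survey or be missed, and the order is not stated.

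**Conclusion.** The point holds as a gap in detection. The plan promises a response to risk written in open survey fields and describes that response, but it does not describe how the text comes to anyone's attention. Followed as written, it allows a remote disclosure to go unread for an unspecified time.

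The size of the harm cannot be given: no review time is stated, the survey-to-interview order is unknown, and the plan itself expects such disclosures to be rare. The number of surveys or open answers measures reading work, not risk. The conclusion assumes that follow-up surveys are remote, as most of the text says, and that the unseen prior-study protocols contain no review step. No endpoint or analysis is affected. This is a cheap improvement for patient safety.

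**What to change.** 1. Beside each open field, in both arms, state that answers are not monitored in real time and show the Lifeline and study clinician numbers. This works whenever the text is read.

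2. Set an automatic alert that sends any non-empty open field to a designated existing staff role for prompt review, within a time that the study clinicians set. A limit counted in business days would leave weekends uncovered, which suits imminent risk poorly. The reader should not be the blind C-SSRS evaluator, because comments about the intervention can reveal the arm. State that disclosures go to the clinician and contact pathway in 1. Risks as well as to adverse event reporting.

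The alert belongs on whichever platform hosts the surveys: METHODS, 7 names REDCap, while METHODS, 4 and 1. Risks describe a study-website account. If the prior-study protocols already contain a review step, cite it here in place of a new one.

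Keep the open-ended items. The cost is a line on the survey pages, an alert setting, a short protocol paragraph and the reading time: up to 192 follow-up surveys, about 12 to 15 a month and 17 to 21 at peak, or up to 256 in all if baseline has open fields. Most answers will be harmless, and clinicians would see only those passed on.
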